No-shows are defined as scheduled appointments that are neither attended nor canceled, and represent a "missed opportunity" on several levels. First, for patients, no-shows may contribute to reduced access and increased wait time. A VA Office of Inspector General audit noted that "reducing unused outpatient appointments could improve timeliness of Veterans' patient care"⁷. Another report found that inefficiencies caused by no-shows in VHA make it "difficult to meet the performance measure of seeing new patients within 30 days"⁴⁰. Second, no-shows contribute to inefficient use of healthcare resources. No-shows result in appointment slots that unexpectedly go unused; further, after a no-show, clinics frequently spend time re-scheduling. The same Office of Inspector General audit estimated that suggested that reducing no-shows in could allow VHA facilities to more efficiently use millions of dollars each year⁷. Third, no-shows represent a missed clinical opportunity. The appointment was scheduled for a clinical reason, which does not get addressed when there is a no-show. Many vulnerable, at-risk groups, including psychiatric patients, ethnic minorities, and low-income patients are disproportionately impacted by no-shows^{4,41,42}, which can contribute to further disparities in clinical outcomes and quality of care^{4,41}.

Why are current approaches to address no-shows in VHA inadequate?

VHA struggles with elevated no show-rates, which have not improved in recent years. VHA's overall no-show rate continues to be approximately 13-14%, far above Secretary Shulkin's stated goal of five percent. In FY2015 this rate led to a total of over nine million no-shows. Despite VHA efforts aimed at reducing no-shows, such as recall scheduling and new patient orientation clinics, no-show rates have been static for years, according to VHA Support Service Center (VSSC) data (see **Figure 1**)¹⁵.

Figure 1. National VA No-Show Rates Between 2013 and 2016

What Veterans are likely to no-show and why?

Research led by our operational partner [name] has described some common characteristics of Veterans who miss visits: mental health and rehabilitation are the service lines with the highest no-show rates; no-show rate increases with age of the appointment (i.e., how long ago it was scheduled); new patients have higher no-show rates; male Veterans have somewhat higher no-show rates than females until age 65, after which it equalizes².

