Our primary outcome will be no-show rate, or the proportion of total appointments that are classified as a no-show, relative to the total number of appointments scheduled. The numerator (“no-shows”) consists of appointments marked as a no-show and appointments canceled by the patient or clinic after the appointment time. The denominator (“total appointments”) consists of no-shows and completed appointments. No-show rates will be measured at the provider-level.

Table 3. Trial Outcomes (Aims 2 & 3)

Outcome	Measure	Data Source
Primary	No-show rate	CDW
Secondary	Cancellation rate	CDW
	Advance cancellation rate	CDW
	Patient-initiated cancellation rate	CDW
Exploratory	Raw wait time	CDW
	Clinically indicated wait time	CDW
	Waiting room time	SHEP
	New mental health appointment wait time	CDW

Our secondary outcome will be cancellation rate, defined as the proportion of scheduled appointments that are marked as canceled. In addition to overall cancellation rate, we will also determine the rate amongst the subset of cancellations that are advance cancellations and patient-initiated cancellations. Advance cancellations, defined here as at least five days before appointment, provide a metric with a reasonable window of time (informed by preliminary data provided by our schedulers) that allows the opportunity to fill a cancelled slot with another waiting Veteran. Patient-initiated cancellations provide a more specific indication of intervention effects on cancellation behavior. Cancellation rates will be measured at the provider-level.

Finally, as exploratory outcomes, we will calculate wait time and number of unique patients seen per day. The latter is simply the number of daily completed encounters, adjusting for patients who have multiple encounters in the same day. For wait time, we will use multiple validated metrics:

- Raw wait time is defined as the length of time in days between the date an appointment was created and the date the appointment was completed⁷⁴. If an appointment is cancelled or a no-show, the wait time will be calculated based on the next appointment that is scheduled and completed in the same clinic stop code.

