effectiveness of interventions varies. For example, we will explore whether the effect of the interventions differ between men and women. To analyze our exploratory outcomes on appointment wait time, we will evaluate time-to-completed appointment using an extended multivariate Cox regression model to account for multiple appointments at the patient level and clustering at the provider level.

Aim 2 Hypotheses: To address Hypothesis 1 (Each intervention group will have a lower no-show rate, as compared with usual care) and Hypothesis 2 (Each intervention group will have a higher cancellation rate, as compared with usual care), we will conduct pairwise comparisons to test for differences between the interventions and usual care as $H_0: \beta_j=0$ for Interventions $j=1,2,3,4$.

Aim 3 Hypothesis (Effect size of nudges will vary by intervention arm such that some categories of nudges have a larger proportional effect than others): We will conduct pairwise comparisons of no-show and cancellation rates by testing the linear combinations between each of the four intervention arms (e.g., Intervention 1 and Intervention 2; $H_0: \beta_1=\beta_2$).

Aim 4: ATLAS.ti software will be used for data management. We will employ a “rapid assessment process,” which is useful for quickly developing understanding from an insider’s perspective and informing future implementation efforts^{81,92}. This multi-step process will be as follows: 1) create domain names for each interview question; 2) create and test a summary template; 3) summarize interview transcripts using the summary template, and 4) transfer summaries into a matrix (respondent x domain) data display⁹³. Our summary template will consist of domains and constructs from our interview guides (i.e., CFIR), and we will compose a templated summary for each interview. We will review these summaries on a regular basis (approximately every five interviews) to ensure interviews build iteratively on emergent findings.

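### A cancellation entered after the appointment time counts as both a no-show and a cancellation, so the overall cancellation rate tested for Hypothesis 2 can mislead if late cancelling differs by arm

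*Combined protocol and SAP*

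**What the plan says.** All references are to the combined protocol and SAP.

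- **Section I, primary outcome.** The no-show numerator is the appointments recorded as no-shows plus "appointments canceled by the patient or clinic after the appointment time". The denominator "consists of no-shows and completed appointments".
- **Section I, secondary outcome.** The cancellation rate is "defined as the proportion of scheduled appointments that are marked as canceled". No time limit is given, and cancellations already counted as no-shows are not excluded.
- **Section I, subsets.** The plan adds that "we will also determine the rate amongst the subset of cancellations that are advance cancellations and patient-initiated cancellations". The advance subset has a time rule: "Advance cancellations, defined here as at least five days before appointment". The patient-initiated subset has none.
- **Section J, Aim 2 Hypotheses.** Hypothesis 2 is tested as "Each intervention group will have a higher cancellation rate, as compared with usual care". The Aim 3 comparisons between interventions also use no-show and cancellation rates.
- **Aims list, Aim 2.** Here Hypothesis 2 concerns the advance cancellation rate, not the overall rate.

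**The concern.** A cancellation entered two hours after the slot began satisfies both definitions in section I. It counts against an arm on Hypothesis 1, where lower is better, and in its favour on Hypothesis 2 as section J words it, where higher is better.

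The plan values cancellation because notice lets the clinic refill the slot. An after-time cancellation gives no such notice, yet it scores as a success. If the letters change how often cancellations are entered late, the overall cancellation rate can miss a real improvement or report one that did not happen.

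The two wordings of Hypothesis 2 make this harder to settle. The version in the Aims is immune to the overlap, and the version in the analysis section is not.

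**Working it through.** **Plan's own figure.** There is none to reproduce: the documents print no share of after-time cancellations. The power figures in section K rest on stop-code rates and provider-level counts that are not printed, and nothing below depends on them.

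**Notation, per arm.** N = scheduled; M = marked no-show; L = cancelled after the appointment time; E = cancelled 0 to 4 days before; V = cancelled at least five days before; C = completed.

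- No-show rate (section I) = (M + L) / (M + L + C)
- Overall cancellation rate as written = (L + E + V) / N
- Overall cancellation rate, before-time only = (E + V) / N
- Advance rate, taken per scheduled appointment = V / N

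The two versions of the cancellation rate differ by L/N. The between-arm difference as written therefore departs from the before-time difference by exactly the between-arm difference in L/N. If L/N is equal across arms, the risk difference is unchanged.

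**Assumed counts per 1,000 scheduled (illustration only).** M = 115, L = 20, E = 80, V = 120, C = 665; total 1,000. Baseline rates:

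- No-show: 135/800 = 16.9%
- Cancellation as written: 220/1,000 = 22.0%
- Cancellation, before-time only: 200/1,000 = 20.0%
- Advance: 120/1,000 = 12.0%

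Three shifts of 20 appointments in an intervention arm, with control at baseline:

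| Shift | No-show rate | Cancellation as written | Before-time only |
|---|---|---|---|
| A. After-time to before-time cancellation | 115/780 = 14.7% | 22.0% (0.0) | 22.0% (+2.0) |
| B. Marked no-show to advance cancellation | 115/780 = 14.7% | 24.0% (+2.0) | 22.0% (+2.0) |
| C. Marked no-show to after-time cancellation | 135/800 = 16.9% | 24.0% (+2.0) | 20.0% (0.0) |

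- **A is a masked gain.** The cancellation rate does not move, although the no-show rate falls. The advance rate rises to 14.0% if the move is to five or more days ahead, and stays at 12.0% otherwise.
- **B is fully captured** under either definition.
- **C is a false gain.** Cancellations rise while the no-show rate is unchanged.

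**Range for A.** Hold total no-shows at 135, vary L from 5 to 40, and let all of L become timely. The rise that the written definition hides is 5/1,000 = 0.5 points to 40/1,000 = 4.0 points. The no-show rate falls from 16.9% to 130/795 = 16.4% and 95/760 = 12.5% respectively.

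**Equal L in both arms, on the model's odds scale.** In B, L is 20 in both arms. The odds ratio as written is (0.24/0.76)/(0.22/0.78) = 1.12. Before-time only it is (0.22/0.78)/(0.20/0.80) = 1.13. A common level of late cancelling therefore barely matters.

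**The case against.** The strongest reply is that the overlap may exist only on paper. Section B lists a single appointment outcome with three values (completed, canceled, no-show). Section I says the metrics follow those of the operational partners and the VHA Support Service Center. The extraction code may already make the categories exclusive. That is possible, but neither statement overrides the explicit rule in section I, and the code is not in the documents.

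Several stronger readings are tempting, and the documents do not support them:

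- *The endpoints of both hypotheses overlap throughout.* They do not. Hypothesis 2 in the Aims uses the advance rate, and an appointment cancelled at least five days ahead cannot also be cancelled after its time.
- *The trial would miss the effect it looks for.* The Background describes patients who cancel instead of not showing. A move from marked no-show to timely cancellation is fully captured (B). Even in A the primary outcome falls.
- *More late cancelling raises the secondary and worsens the primary.* In C the primary is flat. If timely cancellations become late, the primary worsens but the overall cancellation rate does not move. Both happen only if completed visits turn into late cancellations.
- *The inflated level of the cancellation rate rivals the planned effect.* Inflation common to all arms largely cancels. Only a difference between arms biases the comparison.
- *The plan contradicts itself on what a no-show is.* The Background says "No-shows are defined as scheduled appointments that are neither attended nor canceled", but that is description and section I is operational. The two agree once an after-time cancellation is treated as a no-show and not as a cancellation, which is what the fix does.

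**Conclusion.** The double count stands on the wording of section I. It affects the overall cancellation rate, which section J tests for Hypothesis 2 and Aim 3, and the patient-initiated rate when the patient made the late cancellation. It does not affect the primary outcome. It does not affect the advance rate, taken per scheduled appointment like the overall rate.

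The overlap matters only if after-time cancelling differs by arm. Each percentage point of such a difference moves the measured cancellation effect by one point, where section K assumed differences of 1.9 and 2.7 points. Whether any difference exists is unknown. One route is plausible: in section G all four interventions, but not control, carry instructions that invite patients to call and say a message may be left, and a message could be processed after the appointment time. That is inference, and the documents give no figure for it. The 5 to 40 per 1,000 used above is an assumption that shows direction and range, not an estimate.

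This is a worthwhile correction to a tested secondary outcome, not a threat to the trial's main conclusion.

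**What to change.** 1. In section I, limit the numerators of the overall and patient-initiated cancellation rates to cancellations entered before the appointment time. After-time cancellations then count only as no-shows, and each resolved appointment is exactly one of completed, no-show or timely-cancelled.
2. Name the same Hypothesis 2 endpoint, advance or overall, in the Aims list and in section J.

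If the extraction code already excludes after-time cancellations, the first change only records that.

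The cost is a sentence of definition and one aligned hypothesis. No new data are needed, because cancellation timing is already required for the no-show numerator and the five-day rule. Reported cancellation rates become slightly lower and may differ from an operational metric that counts all cancellations.

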Aim 1: Develop and iteratively refine BE-informed messages based on Veterans' perceptions, and incorporate them into enhanced appointment reminders.

Hypothesis: Perceptions of messages will be consistent with our conceptual framework and not associated with emotional harms.

Aim 2: Determine the effect of four versions of enhanced appointment reminders on measures relevant to treatment access, compared with usual reminders.

Hypotheses: 1. Each intervention group will have a lower no-show rate, as compared with usual care. 2. Each intervention group will have a higher advanced cancellation rate, as compared with usual care. Exploratory

Hypothesis: Wait time will be shorter in intervention groups than with usual care.

Aim 3: Evaluate differences in treatment effect associated with four versions of enhanced appointment reminders.

Hypothesis: Effect size of nudges will vary by intervention arm such that some types of nudges will have a larger proportional effect than others.

Aim 4: Characterize potential barriers and facilitators to widespread implementation of enhanced appointment reminder messages. We will conduct semi-structured interviews with key informants (10 Veterans locally and 30 VHA staff nationally). Interview guides will be informed by selected domains and constructs from the Consolidated Framework for Implementation Research.

SCIENTIFIC RATIONALE AND SIGNIFICANCE

BACKGROUND

Why are no-shows a critical health services issue now?

[figure not shown]
Providing and maintaining patient access to care has been declared by leadership as the Veterans Health Administration's (VHA) highest priority. Deficits in access have been shown to contribute to decreased patient satisfaction³⁷, higher mortality rates³⁸ and diminished quality of care³⁹. Amidst an environment of limited access and long wait times, VHA is simultaneously struggling with "no-shows."

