While we anticipate that each intervention arm will have an impact on No-Show rates, it is not clear which messaging combination will have the greatest impact. While we combine some messages, we also anticipate that combining more messages will not have an additive effect. Instead, too many messages may dilute the effectiveness of all the messages. To test this, we developed this intervention arm to include every

message, to determine if behavioral nudges are best used in shorter and smaller combinations.

H. Procedure: Because VHA appointments are managed in the Veterans Health Information Systems and Technology Architecture (VistA) and related data systems, letters and postcards will be designed and formatted within the constraints of VistA and related system requirements. The research team will work with and support clinical application coordinators in mental health and primary care to modify, audit, and maintain letter template changes. Our research team is experienced with staffing resources and procedures necessary in preparing large and customized patient mailings⁸⁵. Because letter templates are unique to each provider and his/her associated clinic(s), the research team will take advantage of this specificity when tailoring messages. Intervention content will be applied to pre-appointment reminder letters and/or postcards, which in VAPORHCS are mailed at the time of scheduling. (Our preliminary data shows that, as of July 2016, in VAPORHCS, appointments are scheduled, on average, 22-33 days before the appointment in primary care and mental health.) In addition, intervention content will also be adapted to no-show letters and/or postcards, which are sent after a no-show, to help reduce risk of repeated no-shows.

I. Measures:

Outcomes for Aim 2
(Determine the effect of four versions of enhanced appointment reminders on measures relevant to treatment access, compared with usual reminders) **and Aim 3** (Evaluate differences in treatment effect associated with four versions of enhanced appointment reminders): **Table 3** summarizes the outcomes used in these Aims.

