These no-show, cancellation, and wait time metrics are consistent with ones used by our operational partners and VSSC. To construct these standardized measures, we will extract administrative data in CDW on appointment/encounter variables, including date, location, provider, stop code, and cancellation remarks. Wait time measures will be stratified based on new vs. established patients. “New patients” are those who have not completed another appointment in a given specialty and parent VA facility during the prior 24 months.

Baseline characteristics (Aims 2 and 3): To demonstrate balance among study arms, we will extract information from CDW on subject demographics (age, sex, race/ethnicity, service connection status, and rurality), diagnoses (proportion with common chronic conditions: depression, PTSD, diabetes, and hypertension), and appointment features (clinic type, new vs. follow-up, provider, and time between appointment creation and actual appointment). We will use protocols and code for data extraction previously established by Drs. [name] and [name] for these variables.

Qualitative assessment (Aim 4): The primary goals of our semi-structured interviews are to identify features of our interventions that act as facilitators or barriers to widespread implementation, and to suggest potential modifications or adaptations to the interventions that would promote larger-scale implementation, long-term maintenance, and adaptability to other reminder modalities. We will develop and pre-test interview guides for VHA staff and Veterans.

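### Raw wait time for a kept visit is set before its letter is mailed, so provider differences in booking lead time blur the exploratory wait-time comparison and the total cannot separate direct from indirect effects

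*Combined protocol and SAP*

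**What the plan says.** The Aim 2 exploratory hypothesis is "Wait time will be shorter in intervention groups than with usual care". Section I (Measures) defines raw wait time as "the length of time in days between the date an appointment was created and the date the appointment was completed". If the visit is cancelled or missed, "the wait time will be calculated based on the next appointment that is scheduled and completed in the same clinic stop code"; the text does not say whether the clock then starts at the first or the second creation date.

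Section H (Procedure) says of pre-appointment letters and postcards "which in VAPORHCS are mailed at the time of scheduling", and reports that "appointments are scheduled, on average, 22-33 days before the appointment in primary care and mental health".

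Section J (Data Analysis) gives one analysis for wait time: "we will evaluate time-to-completed appointment using an extended multivariate Cox regression model", with allowance for repeated visits by a patient and clustering by provider. Section I adds stratification by new versus established patient. No covariate for lead time or earlier wait is named, and no outcome isolates the days added after a missed visit. Section I also lists the interval from booking to visit among the baseline features used to show balance. Section B (Data Source) provides for up to two years of data from before the study start.

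**The concern.** For a kept visit, completion date minus creation date is the booked lead time. That date pair existed when the letter was printed, so the letter cannot have altered it. The plan itself treats the same interval as a baseline feature.

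The letters can reach raw wait by two routes. Directly, they can change the days added when a visit is missed or cancelled. Indirectly, slots released in advance may let later patients be booked sooner, which acts on lead time. The plan adds both into one number. Because the provider is the randomised unit (section F), stable differences between providers in how far ahead they book go into the error of the arm contrast. Allowing for clustering keeps that error honest but does not remove it.

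At stake is the reading of the wait-time hypothesis. A null result could mean that letters do not affect delay, or only that lead-time variation hid a small effect. A positive result could not be assigned to either route.

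**Working it through.** **Plan's own figure.** None is given for wait time. Section K gives power for no-show rate only: primary care >99% at 2.7 points and 82% at 1.9; mental health 80% and 45%. A normal approximation on provider means gives 98.9% and 81.8% in primary care (no-show rate 8%, ρ = 0.04) and 77% and 46% in mental health (15%, ρ = 0.05, 275 providers). Those rates and ρ were chosen to fit, so this shows only that the cluster set-up is of the right order.

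**Inputs from the document.** 150 primary care providers and 157,587 visits a year: 150/5 = 30 per arm, about 1,050 visits each. Mental health: 256/5 ≈ 51 per arm (section K's total; 275/5 = 55 on the other count) and 102,060/275 ≈ 370 visits each. No-show rate 13.5%, the middle of the VHA-wide 13-14%. Effect 2.7 or 1.9 points (section K), or 0.6 (pilot). ρ from 0.02 to 0.05.

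**Assumptions, not in the document.** A miss adds 30 days on average (exponential; provider SD 6). Provider intercept SD 0.3 on the logit scale, so ρ = 0.09/(0.09 + π²/3) ≈ 0.027. Within-provider lead-time SD 20 days. Between-provider SD of mean lead time, L, ranged from 1 to 12 days. Two-sided 0.05.

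**Direct effect, no-shows only.** 0.027 × 30 = 0.81 day. With 22 to 33 days per miss: 0.59 to 0.89 day at 2.7 points, 0.42 to 0.63 at 1.9, and 0.13 to 0.20 at 0.6.

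**Added delay alone.** The variance of a provider's mean is V(p) = 30²[0.3p(1−p)]² + 6²p² + [2·30²p − (30p)²]/m.
- Primary care: V(0.135) = 1.105 + 0.656 + 0.216 = 1.977; V(0.108) = 0.752 + 0.420 + 0.175 = 1.347. SE = √(3.324/30) = 0.333; power Φ(0.81/0.333 − 1.96) ≈ 68%.
- Mental health: 2.373 and 1.669. SE = √(4.042/51) = 0.282; power ≈ 82%.
- Simulation with t-tests gave SE 0.34-0.35 and 0.29, and power about 65% and 80%.

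**Total raw wait.** Add 2(L² + 20²/m) to the sum of the two variances before dividing by providers per arm. Primary care, L = 3: √((3.324 + 18.762)/30) = 0.858.

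| L (days) | PC: SE, power | MH: SE, power |
|---|---|---|
| 1 | 0.45, 44% | 0.40, 52% |
| 2 | 0.64, 25% | 0.53, 34% |
| 3 | 0.86, 16% | 0.69, 22% |
| 5 | 1.34, 9% | 1.05, 12% |
| 8 | 2.10, 7% | 1.62, 8% |
| 12 | 3.12, 6% | 2.40, 6% |

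A provider-clustered log-rank (Cox score) test on simulated visit times gave much the same at L = 2, 3, 5, 8: 23, 15, 10, 7% (primary care) and 32, 22, 15, 7% (mental health).

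**Break-even.** For 80% power the SD of provider mean wait, from all sources, must not exceed (0.81/2.80)√(30/2) = 1.12 days in primary care and (0.81/2.80)√(51/2) = 1.46 in mental health. With 22 to 33 days per miss the limits are 0.8-1.2 and 1.1-1.6 days, against a mean lead time of 22-33 days.

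**Less favourable settings for added delay, still no-shows only.**
- ρ = 0.05 (intercept SD 0.42), 2.7 points: the formula gives 51% and 67%; simulation gave about 45-47% and 63-64%.
- 1.9 points (0.57 day): SE 0.342 and 0.288; 39% and 51% by formula, about 38% and 48% by simulation.
- 0.6 points (0.18 day): about 8-9%.

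**Cancellations.** The next-visit rule covers them too, and Hypothesis 2 expects more of them. Let c be the cancellation rate, assumed 10% to 30%, with the same 30-day delay. V gains 30²[0.3c(1−c)]², and p becomes p + c in its other two terms.
- No letter effect on cancellations: SE 0.50 to 0.87 (primary care) and 0.41 to 0.70 (mental health). Power is 37% to 15% and 50% to 21% by formula; simulation gave 37% to 14% and 46% to 19%.
- Cancellations up 1.9 points: 30 × (0.027 − 0.019) = 0.24 day; power 6-9%.
- Cancellations up 2.7 points: 30 × (0.027 − 0.027) = 0; rejection rate 5%.

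Added delay still has the smaller SE throughout: at c = 30% and L = 3 in primary care, 0.87 against √((22.97 + 18.76)/30) = 1.18.

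**The case against.** The best defence is that the hypothesis concerns access, and access works through booked lead time: a slot released early shortens someone else's wait. On that view lead time is the target rather than noise, and total raw wait is the right measure. Added delay counted over no-shows is roughly the no-show rate times 30 days, so it largely repeats the primary outcome. Counted over cancellations as well, it can be as null as the total, or reversed, under the plan's own hypotheses. Booked lead time, analysed alone, keeps all the provider variance complained of. Raw wait is also only one of four exploratory wait measures in Table 3, and the plan already concedes a weakness in using the creation date.

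Most of this stands. It is why the total should remain the access measure, why no power should be promised for added delay, and why the point is minor. It does not answer the timing argument, and it does not let the total tell the two routes apart.

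A reader might infer that the comparison is biased, or that letters cannot affect raw wait at all. The documents support neither. Randomisation by provider balances lead time in expectation, and both the missed-visit and the freed-slot routes are open.

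**Conclusion.** The point holds as one of precision and interpretability in an exploratory outcome. The timing follows from sections H and I alone. The size rests on assumptions, chiefly the between-provider lead-time SD, which the document does not give; but a spread of provider mean wait of little more than a day is enough to take the total below 80% power for the direct effect of a 2.7-point fall in no-shows.

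It would go too far to say that splitting the outcome makes the hypothesis answerable with good precision. With no-shows only and 30 days per miss, power for added delay at 2.7 points is about 45-65% in primary care and 63-80% in mental health. At 1.9 points it is about 38% and 48%, and it can fall to about 5% if cancellations rise as hypothesised. Nor can a null result on the total be predicted outright, since these figures set the freed-slot effect to zero. If the clock restarts at the replacement visit's creation date, the direct part almost disappears from raw wait. No primary or secondary conclusion is affected. Severity: minor, optional.

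**What to change.** 1. Keep total raw wait time as the access measure.
2. Pre-specify its two parts: booked lead time (creation date to originally scheduled date) and added delay (originally scheduled date to completed date, 0 if kept, truncated at 90 days).
3. Compare each part by arm, with location and a provider random intercept.
4. Report added delay after no-shows and after cancellations separately, because the letters are expected to lower the first and raise the second. Average each over all scheduled visits, so that the comparison stays a randomised one.
5. State that the clock for a replaced visit starts at the original creation date.
6. Adjust total wait and booked lead time for each provider's mean wait in the pre-study data already provided for in section B. Do not adjust for lead time during the trial, which freed capacity could change.
7. Claim no fixed power for any of these.

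The cost is some analysis-plan wording and derived variables from appointment dates already being extracted; trial conduct does not change. The downside is several exploratory wait-time results where there was one, so the text should say that each part is read for its own route and none is confirmatory.
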